3. SUMMARY

- **Title of the project:** ULTRASOUND-GUIDED PERCUTANEOUS TRANSVERSE CARPAL LIGAMENT SECTION VS OPEN SURGERY FOR THE SURGICAL TREATMENT OF CARPAL TUNNEL SYNDROME (CTS).

- **Principal investigator.**

- [name]. F.E.A. Orthopaedic Surgery and Traumatology. University Hospital Complex of Vigo.

- **Centres where the study is planned to be carried out.** University Hospital Complex of Vigo

- **Design.** Prospective observational cohort study.

- **Main and secondary objectives:** To analyze the functional outcome of patients operated on for carpal tunnel syndrome (CTS) in a percutaneous ultrasound-guided manner and compare it with the results obtained by open surgery.

- **Primary endpoint:** Clinical and functional improvement using a specific questionnaire for CTS: Boston Carpal Tunnel Syndrome Questionnaire (BCTQ).

- **Population under study and total number of patients:** Patients from the CHUVI Health Area who have been diagnosed with Carpal Tunnel Syndrome and are going to undergo surgery at the centre from 1 February 2021 to 31 December 2021 by doctors

specialising in Orthopaedic Surgery and traumatology belonging to the CHUVI Upper Limb Unit.

- **Duration of patient enrollment:** From January 1, 2021 to January 31, 2024 (or until the calculated sample size is completed).
- **Calendar and expected date of completion of the study:** February 2024 end of collection; between April and May 2024 analysis and dissemination of results.

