5. HYPOTHESIS OF THE STUDY

Opening of the transverse carpal ligament percutaneously ultrasound-guided for the surgical treatment of carpal tunnel syndrome (CTS) has better results than opening by open surgery (palmar incision).

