7. DESIGN AND METHODS

Design:

Prospective observational cohort study.

Study population:

Patients in the CHUVI Health Area who have been diagnosed with CTS by a specialist in Orthopaedic Surgery and Traumatology at that centre, have undergone surgery for this pathology from 1 January 2021 to 31 January 2024, and meet the inclusion and exclusion criteria.

- Inclusion Criteria:

- 1.- Patient diagnosed with CTS by clinical examination and confirmed by complementary test (Electromyogram).
- 2.- Patients over 18 years of age.
- 3.- Patients who belong to the CHUVI Health Area.
- 4.- Patients with the capacity to consent and who agree to participate by signing the informed consent.
- 5.- Follow the guidelines and reviews set forth in the Consultation.

- Exclusion Criteria:

- 1- Patient who has previously undergone surgery for the same pathology in the same hand (recurrence).
- 2.- Patient incapacitated or unable to follow guidelines indicated by the Physician.
- 3.- Patient with associated pathology in the same hand for which he/she is going to be operated on in the same surgical act.
- 4- Patients with the presence of associated synovitis at the level of the flexor tendons of the hand to be treated.

- Sample size calculation.

Based on the study published by Kim et al²³, who studied the minimum clinically important difference (MCID) for the Boston Carpal Tunnel Syndrome Questionnaire²², and accepting an alpha risk of 0.05 and a beta risk of less than 0.2 in a bilateral contrast,

98 subjects in the first group and 98 in the second group are needed to detect a difference equal to or greater than 0.94 units. The common standard deviation is assumed to be 1. A follow-up loss rate of 10% has been estimated.

Procedure

Patients from the CHUVI Health Area diagnosed with the explained pathology, who meet the inclusion and exclusion criteria, and who are going to undergo surgery at the CHUVI by specialist doctors from the Orthopaedic Surgery and Traumatology Service belonging to the Upper Limb Unit, will be recruited. These patients will be informed of their pathology, and after signing the informed consent, surgery will be performed in the two proposed ways:

-Procedure A: ultrasound-guided percutaneous surgery.

-Procedure B: open surgery through a short palmar incision.

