These two forms of surgical treatment are approved and used in our Service. The assignment to one or another surgical technique will be made based on the criteria of the physician who diagnoses the patient, as he or she does in his or her usual clinical practice, once the patient's clinical characteristics, pathology, and preferences have been heard.

Data will be collected from the patients included in the study in the preoperative consultation, intraoperatively and in the revision consultations that are usually carried out for this pathology 2 weeks after surgery, 6 weeks and 3 months.

In the preoperative consultation, the following will be collected:

- 1.- Grip strength of the hand measured with JAMAR manual dynamometer.
- 2.- Score of the specific questionnaire for the pathology of CTS: Boston Carpal Tunnel Syndrome Questionnaire²² (ANNEX 1).

Surgery will include:

- 1.- Time of surgical intervention
- 2.- Use or not of an ischemia cuff to perform surgery.

In the 2-week postoperative consultation, the following will be assessed:

- 1.- State of surgical wound.
- 2.- Presence of skin infection or other complication.
- 3.- Presence of pillar pain.
- 4.- Absence or presence of CTS (paresthesias or pain in the territory of the median nerve).

In the consultations that will be carried out 6 weeks and 3 months after surgery, the following will be assessed:

- 1.- Surgical incision status.
- 2.- Presence of skin infection or other complication.
- 3.- Presence of pillar pain.
- 4.- Absence or presence of CTS (paresthesias or pain in the territory of the median nerve)
- 5.- Grip strength of the hand measured with a JAMAR manual dynamometer.
- 6.- Score of the specific questionnaire for the pathology of CTS: Boston Carpal Tunnel Syndrome Questionnaire²² (ANNEX 1).

Data recording and management.

Potential candidates who meet the main characteristic of the study will be offered informed consent. Once the consent has been signed, a list of patients who meet the inclusion criteria and none of the exclusion criteria will be created.

The principal investigator ([name] [name]) will be responsible for the collection and custody of the data and will ensure that the pseudonymisation of the participants is maintained. These will be identified through a code in the CRD and in the electronic database, all their information being associated with this code and not with their personal data.

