The other members of the team as third parties involved in the statistical analysis of the data will only have access to the coded information.

Statistical analysis.

A descriptive analysis of the data will be carried out, presenting the qualitative variables with their absolute frequency and percentage, and the quantitative variables with their mean and standard deviation (SD) or median and percentiles if they do not conform to a normal distribution.

Initially, a univariate analysis will be performed to determine which variables could have an independent effect on functional outcomes (grip strength, and the validated questionnaire for CTS: Boston Carpal Tunnel Syndrome Questionnaire ²²).

To compare quantitative variables between the two groups, to assess whether there are differences and whether they are significant, the normality of the distribution of the data in each of the cohorts will be analysed and the parametric t-student test or the

non-parametric test (Mann-Whitney U) will be applied. For the comparison of the qualitative variables between the two cohorts, the Chi-square test will be used.

Subsequently, including as independent variables those that show significance in the univariate analysis or are of clinical interest, they will be included in multivariate regression models.

The data will be analyzed with the SPSS 22.0 Software and 0.05 will be considered as the α accepted significance level for all hypothesis tests.

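### The primary BCTQ endpoint names no visit and no defined score, so with every test at 0.05 either of two visits can carry the main claim, at a 7% to 9% false-positive risk

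*Protocol*

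**What the plan says.** - **Endpoint.** The Summary (section 3) gives the primary endpoint as "Clinical and functional improvement using a specific questionnaire for CTS: Boston Carpal Tunnel Syndrome Questionnaire (BCTQ"). No visit is attached. The main objective (section 6) adds no time point.
- **Hypothesis.** Section 5 states that percutaneous release "has better results than opening by open surgery (palmar incision").
- **Measurement.** Section 7, Procedure, lists the BCTQ before surgery and again afterwards: "In the consultations that will be carried out 6 weeks and 3 months after surgery, the following will be assessed". The item recorded is the "Score of the specific questionnaire for the pathology of CTS", in the singular. The 2-week list has no BCTQ. Neither later visit is called primary.
- **Score.** Annex 1 prints 11 symptom items and 8 activity items, each rated 1 to 5. It gives no scoring rule and no rule for combining the two parts.
- **Planned error rate.** The sample size paragraph of section 7 works by "accepting an alpha risk of 0.05 and a beta risk of less than 0.2 in a bilateral contrast", with subjects "needed to detect a difference equal to or greater than 0.94 units" and a common SD of 1. One difference and one SD are given, tied to no visit or named score.
- **Testing rule.** The statistical analysis paragraph of section 7 says "0.05 will be considered as the α accepted significance level for all hypothesis tests". It describes a t-test or Mann-Whitney comparison first and multivariable regression afterwards, and does not say which result decides.

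**The concern.** The sample size paragraph commits to a 5% false-positive risk for one contrast, and nothing in the protocol identifies that contrast. Two postoperative BCTQ comparisons fit the primary endpoint equally well, and the testing rule gives each the full 0.05. If the groups differ at 6 weeks but not at 3 months, or the reverse, the favourable visit can be presented as the primary result without departing from the protocol. The two visits also answer different questions: early recovery and later outcome.

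At stake is whether a significant result on the main claim carries the error rate that the protocol states. This is separate from bias through the choice of technique ("The assignment to one or another surgical technique will be made based on the criteria of the physician who diagnoses the patient"). Controlling alpha does nothing about that bias, and it comes on top.

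**Working it through.** **Inputs from the protocol**
- Two-sided alpha per test: 0.05 (section 7, statistical analysis), so the critical value is c = 1.96.
- Postoperative visits with a BCTQ score: 2 (section 7, Procedure).
- Scores per visit: 1, taking the singular wording at face value.

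**Assumed input**
- Correlation ρ between the two visits' test statistics. The protocol gives none. The range used is 0.5 to 0.9, since these are repeat scores in the same patients.

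**Step 1. The plan's own error rate.** One named comparison at 0.05 has a false-positive risk of 0.05. This is what the sample size paragraph states, and it holds only if the comparison is fixed in advance.

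**Step 2. Either visit may carry the claim, limiting cases.** If the tests were independent, the risk is 1 − 0.95² = 0.0975. If they were perfectly correlated, it is 0.05.

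**Step 3. Correlated visits.** With standard normal test statistics Z₁ and Z₂ correlated at ρ, and φ and Φ the standard normal density and distribution function,

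risk = 1 − P(|Z₁| ≤ c and |Z₂| ≤ c) = 1 − ∫ φ(x) [Φ((c − ρx)/√(1 − ρ²)) − Φ((−c − ρx)/√(1 − ρ²))] dx, with x from −c to c.

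For errors in favour of percutaneous surgery only, risk = 1 − P(Z₁ ≤ c and Z₂ ≤ c).

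| ρ (assumed) | Two-sided, either visit | Favouring percutaneous only |
|---|---|---|
| one test (plan) | 5.0% | 2.5% |
| 0.9 | 7.0% | 3.5% |
| 0.7 | 8.3% | 4.2% |
| 0.5 | 9.1% | 4.5% |
| independent | 9.75% | 4.9% |

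The two-sided values before rounding are 0.0704, 0.0835 and 0.0907. The independent value in the last column is 1 − 0.975² = 0.0494.

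**Step 4. After the fix.** One score at one visit, decided by one analysis, is one test, and the risk returns to 0.05.

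**Note on the sample size.** The 98 per group does not follow from the stated inputs: 2 × (1.960 + 0.842)² × 1² / 0.94² = 17.8, or 18 per group, and 18/0.9 = 20 after 10% loss. That is a separate matter, and nothing above depends on it.

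**The case against.** **It belongs in the SAP.** Multiplicity handling and model choice are often left to a SAP, and one may exist. This stands for the finer detail. It does not cover the visit and score of the primary endpoint, which are core protocol content. Nor does it cover the 0.05 rule, which this protocol states in its own statistical section.

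**The 0.05 sentence is only a conventional significance level.** True: the protocol nowhere says that either visit may carry the claim. That follows from combining a primary endpoint that has no visit with a rule that gives every test full alpha. The gap permits the choice; it does not announce it.

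**The inflation is modest and rests on assumed correlations.** This also stands. The excess is about 2 to 4 percentage points (7.0% − 5% to 9.1% − 5%), and in a cohort where physicians choose the technique, confounding may matter more.

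Stronger readings that a reader might infer, and why the text does not support them:
- *Four primary tests, because Annex 1 has two parts.* The protocol speaks of one score, one difference and one SD, and never says that the parts are tested separately. The missing scoring rule is a defect, but it does not establish four comparisons.
- *Change and follow-up value as equally open routes.* The word improvement, together with a preoperative score, points to change from baseline, although no sentence says so.
- *A calculable inflation from choosing between the unadjusted test and the regression.* The covariates are to be picked by univariate significance or clinical interest, and baseline BCTQ is not named among them. No rate can be derived from that description.

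**Conclusion.** The point holds. The primary endpoint lacks a visit and a defined score, and the blanket 0.05 rule does not keep the single-contrast risk that the sample size paragraph states. With one score at two visits, the two-sided risk is about 7% to 9% rather than 5% for assumed correlations of 0.9 down to 0.5, and 9.75% if independent.

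These figures assume no true difference at either visit, no confounding, and that significance at either visit would be taken as confirming the hypothesis. They should not be read as the overall false-claim rate of this cohort. The defect should be corrected, but it does not by itself invalidate the study.

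**What to change.** 1. Name one BCTQ score, with its scoring rule, at one visit (for example 3 months) as the single primary comparison, two-sided at 0.05.
2. Tie the 0.94 difference and the SD of 1 to that score and visit.
3. Make the deciding analysis the regression of that score on technique, adjusted for baseline BCTQ and for named confounders that are available. The unadjusted test becomes supportive. In a linear model that includes baseline, the technique coefficient is the same whether the outcome is the follow-up score or the change, so this also settles the form of the endpoint.
4. Label the other visit, and any other BCTQ score, as secondary.

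The amendment should be made before outcomes are compared between the groups.

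**Cost.** The other visit can no longer support the main claim on its own. Under section 8 the change goes back for ethics re-evaluation. Baseline BCTQ and grip strength are already collected, but they are the only items on the preoperative list in section 7. Adjusting for any other confounder would need data recorded elsewhere, so the fix cannot be assumed to be a change of wording alone.

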8. ETHICAL AND LEGAL ASPECTS

Researchers undertake to respect the fundamental principles of the Declaration of Helsinki and the Council of Europe Convention on Human Rights and Biomedicine, as well as all current legislation related to the study.

The handling of the study's data, as well as its database, will comply with the requirements set out in Regulation (EU) 2016/679 and of the European Parliament and of the Council, of 27 April 2016, on the protection of natural persons with regard to the processing of personal data and on the free movement of data. and with Organic Law 3/2018, of 5 December, on the Protection of Personal Data and guarantee of digital rights.

The staff participating in the study will ensure that the anonymity of the participants is maintained. These will be identified through a code in the CRD and in the electronic database, all their information being associated with this code and not with their personal data. All documents will be stored securely and will only be accessible to members of the investigation team and authorized personnel.

The study protocol and all associated documentation will be submitted for evaluation to the Galician ERC Network. Any modifications to the initial approved protocol will be forwarded for re-evaluation.

Informed consent

Study participants must sign an informed consent approved by the Network of Research Ethics Committees (CAEI) of Galicia before any of the study procedures are carried out.

Patients will be provided with a study information sheet and one with informed consent.

It will be clearly stated that the participant is free to withdraw from the study at any time and for any reason without affecting the treatment they will receive in the future and without any obligation to explain the reasons for their withdrawal.

Informed consent will be given to patients in the consultation once they are diagnosed with their pathology, meet the inclusion and exclusion criteria, their pathology is explained to them and participation in the study is offered.

9. IMPLEMENTATION PLAN

Inclusion: January 2021 to January 31, 2024.

Analysis and dissemination: February 2024 to May 2024.

10. FINANCIAL REPORT / SOURCE OF FUNDING

The study has been approved by the Head of the Orthopaedic Surgery and Traumatology Service of the CHUVI.

There is no source of funding.

Date: December 1, 2020

12.- ANNEX 1.- Validated Spanish version of the Boston Carpal Tunnel Syndrome Questionnaire²²

The following questions refer to the patient's symptoms on a typical day (24-hour period) during the past 2 weeks:

A. How severe is your wrist or hand pain at night?

1. I don't have pain in my wrist or hand
2. I have mild pain
3. I have moderate pain
4. I have severe pain
5. I have very severe pain

B. How often do you wake up during a typical night with wrist or hand pain (during the last 2 weeks)?

1. Never
2. Once
3. Two or three times
4. Four to five times
5. More than five times

C. Do you normally have pain in your hand or wrist during the day?

1. No
2. I have mild pain
3. I have moderate pain
4. I have severe pain
5. I have very severe pain

D. How often do you have pain in your wrist or hand during the day?

1. Never
2. Once or twice
3. Three to five times
4. More than five times
5. The pain is constant

E. How long did your last bout of pain last during the day?

1. I never have pain during the day
2. 10 minutes or less
3. 10-60 minutes
4. More than 60 minutes
5. The pain is constant throughout the day

F. Do you have numbness (loss of sensation) in your hand?

1. No
2. I have mild numbness
3. I have moderate numbness
4. I have severe numbness
5. I have very bad numbness

G. Do you have weakness in your hand or wrist?

1. No2. I have mild weakness3. I have moderate weakness4. I have severe weakness5. I have very serious weakness

H. Do you have a tingling sensation in your hand?

1. No2. I have mild tingling3. I have moderate tingling4. I have severe tingling5. I have very bad tingling

I. How serious is the numbness (loss of sensation) or tingling sensation at night?

1. I don't have numbness or tingling2. I have mild numbness or tingling3. I have moderate numbness or tingling4. I have severe numbness or tingling5. I have very bad numbness or tingling

J. How many times did you wake up during a typical night from numbness or tingling of the hand, in the last 2 weeks?

1. Never2. Once3. Two to three times4. Four to five times5. More than five times

K. Do you have difficulty grasping and using small objects such as keys or pens?

1. No2. I have mild difficulty3. I have moderate difficulty4. I have serious difficulty5. I have very serious difficulty

Please answer all answers by circling a number that you think is appropriate.

ACTIVITY	No difficulty	Little Difficulty	Moderate difficulty	Severe difficulty	I can't do anything because of the symptoms
A.- Writing,	1	2	3	4	5
B.- Buttoning clothes,	1	2	3	4	5
C.- Holding a book while reading,	1	2	3	4	5
D.- Grab a phone,	1	2	3	4	5
E.- Open jars	1	2	3	4	5
F:- Do household chores	1	2	3	4	5
G:- Carry shopping bags	1	2	3	4	5
H.- Bathing and dressing	1	2	3	4	5

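### The annexed BCTQ does not say which hand to answer for and the other hand is never recorded, so contralateral disease or surgery can enter the primary outcome and cannot be adjusted for

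*Protocol*

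**What the plan says.** The Summary makes clinical and functional improvement on the BCTQ the primary endpoint. Section 7 (Procedure) has the form completed preoperatively, at 6 weeks and at 3 months.

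**The form (Annex 1).** The symptom part fixes a recall period: "The following questions refer to the patient's symptoms on a typical day (24-hour period) during the past 2 weeks". It does not fix a hand. The first item is typical: "How severe is your wrist or hand pain at night". The other symptom items likewise name no side. The function part is introduced by "Please answer all answers by circling a number that you think is appropriate", again without a side, and includes opening jars, fastening buttons and "H.- Bathing and dressing".

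**Eligibility (section 7).** Exclusion 1 concerns earlier surgery on the same hand. Exclusion 3 reads "Patient with associated pathology in the same hand for which he/she is going to be operated on in the same surgical act". Exclusion 4 reads "Patients with the presence of associated synovitis at the level of the flexor tendons of the hand to be treated". Exclusion 2 is about capacity and adherence. No criterion addresses the other hand.

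**Data collected (section 7, Procedure).** The preoperative, surgical and follow-up lists contain no item on CTS in the other hand and none on hand surgery since the index operation. The follow-up item on persisting CTS symptoms also names no side.

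**Allocation and analysis (section 7).** The diagnosing physician chooses the technique after hearing the patient's preferences. Variables that are significant in univariate analysis, or of clinical interest, may enter the regression models.

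**The concern.** The treatment acts on one hand, but the outcome is a patient's answer about an unspecified one. A patient with symptoms in both hands is eligible. After a fully successful release, that patient can truthfully report night pain, numbness or trouble with two-handed tasks because of the other hand. The same holds for a patient whose other hand is operated on before the 6-week or 3-month form.

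In a randomised trial this would mostly add noise or pull the estimate towards zero. Here the technique is chosen, so the frequency of contralateral disease or surgery need not be equal in the two cohorts, and any difference would be credited to the technique. The planned regression cannot repair this, because a variable that was never recorded cannot be entered. Nor can a later analysis plan recover which hand a patient had in mind. The form and the data fields are set in this protocol, so this is the place to settle the matter.

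The point concerns contamination of the score in a patient counted once. Whether two hands of one patient may be counted as independent is a different question.

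**Working it through.** **1. Search for a rule on side.** Endpoint, form, exclusions, data lists and analysis text were read against each other.

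| Place | What is fixed | Other hand covered? |
|---|---|---|
| Summary, primary endpoint | BCTQ improvement | No |
| Annex 1, symptom items | Past 2 weeks | No |
| Annex 1, function items | Circle a number | No |
| Exclusions 1, 3, 4 | Operated hand | No |
| Exclusion 2 | Capacity, adherence | No |
| Data lists, all visits | Score, grip, wound, symptoms | No |
| Statistical analysis | Clinically relevant covariates allowed | Only if recorded, and it is not |

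**2. Yardstick from the protocol.** Section 7 plans 98 per group, 10% loss, SD 1 and a difference of 0.94 at two-sided 0.05. The usual formula with these inputs and 80% power gives 2 × (1.96 + 0.84)² / 0.94² ≈ 17.8, so 18 per group, or 18 / 0.9 = 20 with loss. It does not give 98. That is a separate matter; 98 is used here only as the planned size.

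- Evaluable per group: 98 × 0.9 ≈ 88
- Standard error of the difference: 1 × √(2/88) = 0.151
- Observed difference needed for significance: 1.96 × √(2/88) = 0.295 units

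The protocol does not say whether the SD of 1 refers to a score or to a change; it is used as stated.

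**3. What survives in change from baseline.** Suppose the other hand adds *c* units to the score.

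- If *c* is the same before and after surgery, change = (follow-up + *c*) − (baseline + *c*), and *c* drops out.
- If the worse hand drives the answer, the other hand hides part of the improvement. This does not cancel.
- If the other hand is operated on after baseline, its effect is in the follow-up score only. This does not cancel.

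Only the last two give a net shift.

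**4. Unequal frequency between cohorts (assumed values).** Spurious difference = imbalance × net shift. The last column is the chance of a significant result in that direction with no true effect (nominal 2.5%).

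| Imbalance | Net shift | Spurious difference | Chance |
|---|---|---|---|
| 0.10 | 0.5 | 0.05 | 5.2% |
| 0.10 | 1.0 | 0.10 | 9.7% |
| 0.20 | 0.5 | 0.10 | 9.7% |
| 0.20 | 1.0 | 0.20 | 26.3% |
| 0.30 | 0.5 | 0.15 | 16.7% |
| 0.30 | 1.0 | 0.30 | 51.2% |

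Only the last row reaches 0.295.

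**5. Equal frequency (assumed values).** An additive shift gives no bias, only more spread. Masking shrinks the contrast to 0.94 × (1 − *q* × *f*), where *q* is the share of patients affected and *f* the share of their contrast that is hidden.

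- *q* = 0.2, *f* = 0.5: 0.846, power above 0.99
- *q* = 0.6, *f* = 0.5: 0.658, power 0.99
- *q* = 0.6, *f* = 1: 0.376, power 0.70

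**The case against.** The wording without a side comes with what Annex 1 calls the validated Spanish version. Several symptom items speak of the hand in the singular, and the form is completed at visits devoted to the treated hand, next to its incision and its grip strength. Most patients may well answer for that hand, and staff may tell them to. The documents give no rate of bilateral CTS, no practice of operating on the second hand within 3 months, and no sign that bilateral disease guides the choice of technique. Covariate lists and sensitivity analyses often belong in an analysis plan, which is not at hand.

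Much of this stands, and it limits what may be said:

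- A reader might infer that contralateral disease does distort the results. The documents support only that it can.
- A reader might apply a larger shift to the follow-up score alone, for example 1.5 units, giving 0.30 × 1.5 = 0.45. That shift exceeds the plan's own target difference of 0.94, and it overlooks that a stable contribution largely cancels against the preoperative score.
- A reader might infer that dilution endangers the planned test. Step 5 shows that it hardly does unless masking is both common and complete.

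What does not stand is leaving the matter to a later plan. No written rule tells the patient which hand to score, and a later plan can neither restore the side nor adjust for a status that was not collected.

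**Conclusion.** The gap is real: the primary outcome as printed is not tied to the operated hand, and the other hand is neither excluded nor recorded. In a comparison where the technique is chosen, this opens a route to confounding that the planned models cannot close.

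Its size is unknown. The range of 0.05 to 0.30 units rests on assumed net shifts of 0.5 to 1.0 and assumed imbalances of 10 to 30 points, with 88 evaluable per group and SD 1. Only the upper end reaches the significance threshold of about 0.295, and all of it lies well below 0.94. The material risk is therefore a small spurious difference, or a result whose meaning is unclear. Loss of power is not the main worry, and nothing shows that the comparison is already invalid. This is a cheap improvement, well worth making because it cannot be made afterwards.

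**What to change.** 1. **Annex 1:** add a line at the head of both parts telling the patient to answer for the hand operated on in this study. The items themselves stay unchanged.
2. **Preoperative data:** record CTS in the other hand (yes/no).
3. **6 weeks and 3 months:** record the date and type of any other hand surgery since the index operation.
4. **Statistical analysis:** name contralateral CTS and baseline BCTQ as covariates in the adjusted comparison, whatever the univariate screen shows.
5. **Sensitivity analysis:** repeat the primary comparison without BCTQ scores obtained after another hand operation. It should stay secondary, because the omission depends on an event after surgery.

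The cost is one instruction, two data fields, two prespecified covariates and one extra analysis. Eligibility and care are untouched. The limitation is that tasks done with both hands cannot be made fully side-specific, so some contamination of the function part will remain and should be acknowledged in the report.
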